#### *On-going clinical studies*

ISO-MTX-003 is an open-label, multicenter, phase I/II non-IND clinical study designed to identify the Modufolin® for Injection, 100 mg dose with the most favorable safety prospect and confirmed ability to mitigate HDMTX induced toxicity during treatment of osteosarcoma patients. The study was designed to (i) investigate the safety of Modufolin® rescue therapy, (ii) identify a recommended dose for further study, (iii) and evaluate the feasibility of Modufolin® as rescue therapy for HDMTX treatment.

ISO-CC-005 is an open-label, multi-site, phase I/II non-IND clinical dose cohort study which will investigate the tolerability of Modufolin® for Injection, 100 mg in combination with a fixed dose of 5-FU alone or together with a fixed dose of Oxaliplatin or Irinotecan in patients with stage IV colorectal cancer. Toxicity will be evaluated for 4 dose levels (30, 60, 120 and 240 mg/m^2) in 5 treatment arms, see treatment regimen below:

#### Modufolin® for Injection, 100 mg:

Arm 1: 30, 60, 120 and 240 mg/m^2.

Arm 2-3: 30 and 60 mg/m^2 *i.v.* bolus injection, twice q2w (*i.e.*, on Day 1 and Day 2 of each chemotherapy cycle)

Arm 4: 60, 120 and 240 mg/m^2 *i.v.* bolus injection, Day 1 only of each chemotherapy cycle). Enrolment in next dose cohort if the lower dose shows favorable tolerability.

Arm 5: Selected Phase 2 dose from Arm 4.

#### Chemotherapies (4 cycles over 8 weeks):

Arm 1: 5-FU (500 mg/m^2) alone

Arm 2: 5-FU (500 mg/m^2) and Oxaliplatin (85 mg/m^2)

Arm 3: 5-FU (500 mg/m^2) and Irinotecan (180 mg/m^2)

Arm 4: 5-FU (400 mg/m^2+2400 mg/m^2) and Oxaliplatin (85 mg/m^2)

Arm 5: 5-FU (400 mg/m^2+2400 mg/m^2) and Oxaliplatin (85 mg/m^2) + bevacizumab (5 mg/kg)

For further details on completed and on-going clinical studies, refer to the Investigator's Brochure (IB).

A summary of safety and PK data from Isofol Medical AB's previous clinical studies on Modufolin® for Injection, 100 mg in cancer patients is provided in Appendix 18.3.

### **7.3 Risk/benefit assessment**

Modufolin® for Injection, 100 mg is a stable formulation of the naturally occurring diastereoisomer of MTHF, the endogenous co-substrate of thymidylate synthase which is involved in the enzymatic pathway of nucleotide substrates necessary for DNA synthesis.

Based on available data to date, the occurrence of any adverse reactions due to Modufolin® for Injection, 100 mg alone is not expected. Modufolin® for Injection, 100 mg has been safely administered to 72 patients at doses between 7.5 and 500 mg/m^2 with no serious side-effects specifically related to Modufolin® for Injection, 100 mg alone. There is no evidence that Modufolin® for Injection, 100 mg may be of safety concern for patients, either after administration of repeated doses or after administration of single high doses. No SAEs assessed as possibly related to Modufolin® for Injection, 100 mg alone have been reported. Consequently, all SAEs assessed as having a possible relationship to Modufolin® for Injection, 100 mg should be reported as Suspected Unexpected Serious Adverse Reactions (SUSARs).

A review of the safety data from the non-IND clinical studies ISO-MC-091, ISO-CC-002, ISO-MTX-003 and ISO-CC-005 identified fatigue and nausea as the most common AEs assessed as possibly related to study treatment. However, these events were no more frequent than could be expected for the same cytotoxic agents in the presence of other folates.

### 7.3.1 Summary of risk management

As the healthy volunteers in this study will have no medical benefit from participation, their safety and well-being is of utmost importance.

The subjects will however remain at the research clinic for 24 hrs after the administration of the IMP/placbeo and will be closely monitored by medical staff. A final safety check will take place at a Follow-up visit scheduled 5 to 10 days after dose administration.

The Principal Investigator at the research clinic will ascertain that adequate facilities and procedures are available to handle emergency situations should they occur during the study. The medical staffs at CTC Clinical Trial Consultants AB (hereafter referred to as CTC) have extended experience from early Phase I studies and there are adequate procedures in place to handle unexpected and expected adverse reactions in the study subjects.

There can be risks related to medical devices used in the study *e.g.*, indwelling venous catheters, but they are devices used in routine medical care and the risk is considered low and ethically justifiable. Study specific evaluations and sampling procedures like blood-pressure measurements using a blood pressure cuff and frequent blood-sampling, can cause transient discomfort but the risk is deemed to be low and ethically justifiable.

The use and frequency of the above mentioned risk factors have been kept at a low level that still will meet the scientific and medical goals for the study and at the same time not expose the healthy volunteers participating in the study for risks that would not be ethically justifiable.

## 8 STUDY OBJECTIVES AND ENDPOINTS

### 8.1 Primary objective

To evaluate effects on ECG parameters after single ascending doses of Modufolin® for Injection, 100 mg in healthy male volunteers

#### 8.1.1 Primary endpoints

The primary evaluation parameter is:

- Change-from-baseline QTcF ( $\Delta$ QTcF)

### 8.2 Secondary objectives

To evaluate safety, tolerability and PK following single ascending doses of Modufolin® for Injection, 100 mg in healthy male volunteers

#### 8.2.1 Secondary endpoints

The secondary evaluation parameters are:

- Change-from-baseline heart rate, PR and QRS interval ( $\Delta$ HR,  $\Delta$ PR and  $\Delta$ QRS)
- Categorical outliers for QTcF, HR, PR interval, QRS interval;
- Categorical analysis for T wave morphology;
- Relationship between Modufolin® plasma concentration and  $\Delta\Delta$ QTc
- Frequency, seriousness and intensity of AEs
- Physical examination
- Vital signs
- Safety laboratory measurements
- Plasma PK characteristics of Modufolin® for Injection, 100 mg and its metabolites:
  - [6R]-5,10- Methylene Tetrahydrofolate (MTHF; Modufolin® for Injection, 100 mg)
  - [6S]-5-Methyl-Tetrahydrofolate (5-Methyl-THF)
  - [6S]-Tetrahydrofolate (THF)
  - [6S]-5-Formyl-Tetrahydrofolic acid (5-Formyl-THF)

The PK parameters to be evaluated are listed in Section [17.7.5](#).

## 9 INVESTIGATIONAL PLAN

### 9.1 Overall study design and schedule of events

An adaptive randomised, double-blind, single-centre, placebo-controlled Phase I study evaluating ECG effects, safety, tolerability and PK of single ascending doses of Modufolin® for Injection, 100 mg in healthy male volunteers.

Thirty-three (33) eligible and consenting subjects will be included in 3 cohorts, 11 subjects in each cohort. Within each cohort, subjects will be randomised to receive either placebo (3 subjects) or Modufolin® for Injection, 100 mg (8 subjects).

There will be 3 pre-defined ascending dose-levels. Additional dose levels may be considered if recommended by the internal Safety Review Committee (iSRC; see Section 9.1.2). There will be an interval of at least 7 days between each dose level to allow time for safety data to be analyzed and evaluated by the iSRC. The iSRC will have the choice to decide to escalate the dose as planned, reduce or increase the dose escalation step, repeat the dose, reduce the dose or terminate the study.

The total study duration for the subjects will be approximately 5 weeks and there will be in total 3 visits to the clinic. Subjects will be screened for eligibility according to study-specific inclusion/exclusion criteria (see Sections 10.4 and 10.5) within 4 weeks prior to start of study treatment (Visit 1; Screening visit). The subjects will be confined to the research clinic from the evening before dosing (Day -1) until 24 hrs post dose (Days 1 and 2). The subjects should be fasting overnight (8 hrs) before IMP/placebo administration until 4 hrs post-dose. A Follow-up Visit will be performed 5 to 10 days after dose administration of for each cohort.

The timing of all study assessments is shown in the Schedule of events provided in Table 1.

Further details about the randomization procedures are presented in Section 10.8, procedures for maintaining the blind in Section 10.9 and treatment administration in Section 11.6.

Table 1 Schedule of events (2 pages)

Visit number	1												2												3	
	Screening												In-clinic period												FU	
Day	-28 to -1		-1		1												2		6 to 11							
Time points	-		-2 h	-45 min	-30 min	-15 min	0	5 min	15 min	30 min	1 h	2 h	3 h	4 h	5 h	6 h	8 h	12 h	24 h	-						
Time windows (min)	-	-	-	±2	±2	±2		±2	±2	±2	±5	±5	±5	±5	±5	±5	±5	±5	±5	±60	-					
Informed consent	x																									
Demographics	x																									
Medical/surgical history	x																									
Inclusion/exclusion criteria	x	x																								
Physical examination	x																			x						
Weight	x	x																								
Height	x																									
Vital signs (BP and pulse)	x					x										x		x		x		x	x			
Hematology, clinical chemistry	x		x 																		x	x				
Urine analysis (dip stick)	x	x																								
HIV, hepatitis B and C	x																									
Drugs of abuse	x	x																								
Alcohol screen	x	x																x		x		x		x		
12-lead safety ECG 	x		x 														x		x		x		x	x		

Visit number	1		2																		3			
	Screening		In-clinic period																		FU			
Day	-28 to -1		-1		1																		2	
Time points	-		-2 h	-45 min	-30 min	-15 min	0	5 min	15 min	30 min	1 h	2 h	3 h	4 h	5 h	6 h	8 h	12 h	24 h	-	-	-	-	
Time windows (min)	-	-	-	±2	±2	±2		±2	±2	±2	±5	±5	±5	±5	±5	±5	±5	±5	±5	±60	-	-	-	-
Holter ECG (Cardiodynamic) 			x 	x	x	x	x	x	x	x	x	x	x	x	x	x	x	x	x	x	x	x	x	
Randomisation			x																					
IMP/placebo administration								x 																
PK blood sampling 					x		x	x	x	x	x	x	x	x	x	x	x	x	x	x	x	x	x	
AE reporting		x	x	x	x	x	x	x	x	x	x	x	x	x	x	x	x	x	x	x	x	x	x	
Prior and concomitant medication	x	x	x	x	x	x	x	x	x	x	x	x	x	x	x	x	x	x	x	x	x	x	x	

FU=Follow-up Visit; min=minutes; h=hour; BP=Blood Pressure; ECG=Electrocardiogram; IMP=Investigational Medicinal Product; PK=Pharmacokinetic; AE=Adverse Event

 Within 1 hr prior to dose administration.

 Safety ECGs will be printed on-site and interpreted by the Investigator. Pre-dose safety ECGs in triplicate will be extracted within 1 hr prior to dose administration.

 Continuous 12-lead ECG recording (Holter ECG) will start 2 hrs prior to dose administration on Day 1. Holter ECGs will be extracted at 3 time points before dosing (-45, -30 and -15 min). Subjects will be supinely resting for at least 10 min prior to time points for ECG recordings. When time points for ECG recordings coincide with other assessments, procedures should be carried out in the following order: (1) Holter ECG, (2) safety ECG, (3) vital sign, (4) PK blood sampling and (5) safety blood sampling.

 Subjects should be fasting overnight (8 hrs) before IMP/placebo administration and until 4 hrs post-dose.

 Time 0 = end of IMP/placebo infusion. For further information on the PK blood sampling procedures, refer to Section 13.1.

### 9.1.1 Dose levels

The proposed dose levels are 200, 350 and 500 mg/m^2 Modufolin® for Injection, 100 mg.

Each dose will be administered as a single bolus *i.v.* injection.

Depending on results obtained during the study, the number of dose levels, the actual dose, frequency of dosing and planned sampling times might have to be adjusted. These adjustments will be documented in non-substantial amendments to the CSP.

The study maximum dose (SMD) will not exceed 500 mg/m^2 administered as single bolus *i.v.* injection.

### 9.1.2 Internal Safety Review Committee

The iSCR will consist of:

- The Principal Investigator or delegate
- A Sponsor Medical representative or delegate

Additional internal or external experts may be consulted by the iSCR if needed.

After each completed dose level, the iSCR will evaluate all available safety data. The decision may be to give the next intended dose, a greater or smaller dose increment than the intended dose, a repeated dose, a lower dose or to stop dosing.

A dose escalation beyond 500 mg/m^2 will not be mandated by the iSRC unless authorized by the regulatory authority in a substantial amendment to this CSP.

The randomization code may be broken by the iSRC during the assessment process (partial un-blinding) but only for subjects with severe AEs ( $\geq$ grade 3) to enable their decision on continued dosing of further cohorts or to stop the dose escalation. The medical staff and the subjects will remain blinded for the treatments (active drug or placebo) to be administered in the subsequent dose groups/cohorts in order to minimize bias.

The decision of the iSRC on the next dose level will be taken in consensus between the iSRC members and documented appropriately in a safety evaluation form provided by CTC.

### 9.1.3 Stopping criteria for dose escalation

The Principal Investigator and the iSRC will follow the recommendations and grading system of Common Terminology Criteria for Adverse Events (CTCAE) v4.03 (see Section 12.5.2.1) but also take into account the recommendations published by M Sibille *et al.* 2010^10 which is an adaptation to FIH studies of the grading systems previously proposed by National Cancer Institute (NCI), World Health Organization (WHO), National Institutes of Health (NIH) and Food & Drug Administration (FDA). The grade, the frequency of AEs and the blinding will be taken into account.

At the individual level, basically, a Grade 2 AE is at minimum a safety alert leading to caution and closer assessment of safety in other subjects. An escalation to Grade 3 applies if rapid worsening, concomitant findings, clinical symptoms and signs occur. A Grade 3 AE always supports stopping the suffering subject from continuing participation in the study.

At the dose group level, the algorithm supporting the stopping rules to be strictly followed is presented in Table 2. An un-blinding, limited to suffering subjects, will be applied. A 33%

frequency of AEs or findings (Grade 3 or 2, as explained above) of the same types will trigger a stop of dose escalation. However, depending on the type and potential risk of the AE, any modulation can be decided, for example, for safety concerns, a lower frequency level. Following the iSRC risk evaluation of AEs (Grade  $\geq 3$ ) it may be decided to, for the next dose level to either repeat the current dose level, lower the dose or stop dosing.

**Table 2 Dose escalation and stopping rules**

If 0/11  subjects have Dose Limiting Toxicity (DLT)	Escalate to the next higher dose level	No un-blinding
If 1/8 subjects on active drug has DLT	Repeat the current dose level or escalate to the next higher dose level	Partial un-blinding (of subjects with DLT)
If $\geq 2/8$ subjects on active drug have DLT	Stop further dosing	Partial un-blinding (of subjects with DLT)

 Control subjects included

## 9.2 Rationale for study design and dose groups

A Single Ascending Dose (SAD) design was chosen for the evaluation of the cardiac safety of Modufolin® for Injection, 100 mg. The adaptive study design allows for flexible dose escalation and involves careful monitoring of the subject's well-being. The study will also provide important PK data to support the design of further studies, both in healthy volunteers and in patients. The time points for PK blood sampling were selected based on data obtained from previous clinical studies (see summary of PK data in Appendix 18.3). After dose administration, the time points for extraction of ECG data are paired with PK blood sampling.

A placebo control will be used to establish the frequency and magnitude of changes in endpoints that may occur in the absence of active treatment.

Randomization will be used to minimize bias in the assignment of subjects to dose groups and to increase the likelihood that known and unknown subject attributes (e.g., demographic and baseline characteristics) are evenly balanced across treatment groups.

Blinded treatment will be used to reduce potential bias during data collection and evaluation of endpoints.

The primary objective of the current clinical study is to evaluate potential effects on ECG parameters following single doses administration of Modufolin® for Injection, 100 mg in healthy volunteers. To allow exclusion of a small effect on the QT interval, serial ECG monitoring is implemented in the study, a highly precise ECG methodology will be used and data will be analysed using exposure response analysis.

Three dose levels of Modufolin® for Injection, 100 mg will be studied (200, 350 and 500 mg/m^2), including two supratherapeutic doses, which will obviate the need for a positive control in the study. Based on current data the expected clinical dosing regimen in future clinical trials in metastatic colorectal cancer patients (lead indication) is 120 mg/m^2 Modufolin® for Injection, 100 mg. Doses of Modufolin® up to 500 mg/m^2/day have been administered to patients in a previous non-IND clinical study with no safety concerns (ISO-MC-091).

## 10 STUDY POPULATION

### 10.1 Recruitment

The subjects will be recruited from a database of healthy volunteers at CTC and from advertising in media including social media.

### 10.2 Screening and enrolment log

A screening number will be allocated to each subject undergoing screening. The Investigator will keep records of all subjects screened and included. The reason for screen failure should be stated for all subjects screened but not included. The reason for withdrawal should be stated for all subjects included but not completed.

If a subject cannot receive the planned dose of IMP/placebo within 28 days after screening (*i.e.*, the time interval between signing informed consent until dose administration, the subject should be rescreened before proceeding in the study).

### 10.3 Number of subjects

Thirty-three (33) male subjects will be included in the study.

To account for potential drop-outs and/or additional cohorts depending on PK data and recommendations from the iSRC, additional male subjects might be included in the study (see Section 9.1.2).

For replacements of subjects discontinuing the study, see Section 10.7.1.

### 10.4 Inclusion criteria

For inclusion in the study, subjects must fulfil the following criteria:

1. Willing and able to provide a written informed consent for participation in the study.
2. Healthy male subject aged 18-60 years inclusive.
3. Body Mass Index (BMI)  $\geq 18$  and  $\leq 30 \text{ kg/m}^2$  and weight at least 50 kg and no more than 100 kg at screening and body surface area  $\leq 2 \text{ m}^2$ .
4. Clinically normal medical history, physical findings, vital signs, ECG and laboratory values at the time of screening, as judged by the Investigator.
5. Willing to use condom and highly effective contraceptive methods with a failure rate of  $< 1\%$  to prevent pregnancy and drug exposure to a partner and refrain from donating sperm from the date of dosing until 3 months after dosing of the IMP/placebo.

---

 Combined (estrogen and progestogen containing) hormonal contraception associated with inhibition of ovulation (oral, intravaginal, transdermal), progestogen-only hormonal contraception associated with inhibition of ovulation (oral, injectable, implantable), intrauterine device (IUD), intrauterine hormone-releasing system (IUS), bilateral tubal occlusion, vasectomized partner/vasectomy, sexual abstinence.

## 10.5 Exclusion criteria

Subjects must not enter the study if any of the following exclusion criteria are fulfilled:

1. History of any clinically significant disease or disorder which, in the opinion of the Investigator, may either put the subject at risk because of participation in the study, or influence the results or the subject's ability to participate in the study.
2. Any clinically significant illness, medical/surgical procedure or trauma within four weeks of the first administration of IMP/placebo.
3. Any planned major surgery within the duration of the study.
4. Any positive result on screening for serum hepatitis B surface antigen, hepatitis C antibody and Human Immunodeficiency Virus (HIV).
5. After 10 minutes (min) supine rest at the time of screening, any vital signs values outside the following ranges:
  - Systolic BP > 150 mm Hg
  - Diastolic BP > 90 mm Hg
  - Pulse < 40 or > 85 beats per min
6. Prolonged QTcF (>450 ms), cardiac arrhythmias or any clinically significant abnormalities in the resting ECG at the time of screening, as judged by the Investigator.
7. History of severe allergy/hypersensitivity or on-going allergy/hypersensitivity, as judged by the Investigator, or history of hypersensitivity to drugs with a similar chemical structure or class to Modufolin® (*i.e.*, folate derivatives).
8. Regular use of any prescribed or non-prescribed medication including antacids, analgesics, herbal remedies, vitamins and minerals within two weeks prior to the administration of IMP/placebo, except occasional intake of paracetamol (maximum 2000 mg/day; and not exceeding 3 000 mg/week), at the discretion of the Investigator and nasal decongestants without cortisone or antihistamine for a maximum of 10 days, at the discretion of the Investigator.
9. Regular use of any prescribed or non-prescribed medication which could influence folate and vitamin B12 status within 30 days prior to the administration of IMP/placebo.
10. Administration of another new chemical entity (defined as a compound which has not been approved for marketing) or has participated in any other clinical study that included drug treatment with less than three months between administration of last dose and first dose of IMP/placebo in this study. Subjects consented and screened but not dosed in previous phase I studies are not excluded.
11. Current smokers or users of nicotine products. Irregular use of nicotine (*e.g.*, smoking, snuffing, chewing tobacco) less than three times per week is allowed before screening visit.
12. Positive screen for drugs of abuse or alcohol at screening or on admission to the unit prior to administration of the IMP/placebo.
13. Current or history of alcohol abuse and/or use of anabolic steroids or drugs of abuse.

14. Intake of xanthine and/or taurine containing energy drinks within two days prior to screening.
15. Plasma donation within one month of screening or blood donation (or corresponding blood loss) during the three months prior to dosing.
16. Investigator considers the subject unlikely to comply with study procedures, restrictions and requirements.

## 10.6 Restrictions during the study

### 10.6.1 General restrictions

- **Contraception Requirements:** The male volunteers are expected to use condom and other effective contraceptive methods with a failure rate of < 1% to prevent pregnancy and drug exposure of a partner and refrain from donating sperm from the date of dosing until 3 months after last dosing of the IMP/placebo.
- **Meals and Dietary Restrictions:** Study subjects will receive standardized meals during study days at the clinic. No breakfast will be served before dose administration. Lunch will be served 4 hrs post-dose, a snack at 6 hrs post-dose and dinner 9 hrs post-dose. Water is allowed ad libitum at the clinic.
- **Fasting:** The subjects should be fasting overnight (8 hrs) before IMP/placebo administration until 4 hrs post-dose.
- **Alcohol:** Consumption of alcohol is not allowed within 48 hrs prior to all clinic visits until after the Follow-up Visit.
- **Coffee:** Consumption of up to five cups of coffee per day will be allowed during the study.
- **Xanthine or taurine containing products/beverages:** Energy drinks (e.g., Redbull) are not allowed during the study.
- **Nicotine:** Smoking or use of nicotine-containing products is not allowed during the study.
- **Grapefruit and grapefruit containing products:** Consumption of grapefruit and/or grapefruit containing products is not allowed during the study.
- **Exercise:** The subjects must refrain from strenuous exercise (defined as greater than 70% of the maximal pulse rate for one hour or more) during the study.
- **Blood donation:** The subjects must not donate blood or plasma during the study until three months after the final medical examination at the Follow-up Visit.

---

 Combined (estrogen and progestogen containing) hormonal contraception associated with inhibition of ovulation (oral, intravaginal, transdermal), progestogen-only hormonal contraception associated with inhibition of ovulation (oral, injectable, implantable), intrauterine device (IUD), intrauterine hormone-releasing system (IUS), bilateral tubal occlusion, vasectomised partner, sexual abstinence.

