## 17.4 Electrocardiogram analysis

### 17.4.1 Baseline

For all ECG parameters, baseline is defined as the average of the measured QTc intervals from the 3 pre-dose time points (45, 30, and 15 min pre-dose) on Day 1.

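### Section 10.6.1 sets no coffee rule for the confined ECG day, so the 5 to 24 h Holter points are open to self-chosen, unrecorded caffeine

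*Protocol*

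**What the plan says.** The relevant rules sit mostly in Protocol section 10.6.1.

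- Coffee: "Consumption of up to five cups of coffee per day will be allowed during the study". There is no timing rule and no exception for the days in the clinic.
- Xanthine or taurine products: the bullet's heading covers products and beverages in general, but its text bars only energy drinks: "Energy drinks (e.g., Redbull) are not allowed during the study".
- Fasting: "The subjects should be fasting overnight (8 hrs) before IMP/placebo administration until 4 hrs post-dose". Breakfast is not served before dosing, and lunch comes at 4 h.
- Drinks in the clinic: "Water is allowed ad libitum at the clinic". Meals are standardised. Coffee is mentioned neither in the meal rule nor in the fasting rule.

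Elsewhere in the protocol:

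- Section 10.5, exclusion 14, concerns "Intake of xanthine and/or taurine containing energy drinks within two days prior to screening".
- Table 1, note 3: "Continuous 12-lead ECG recording (Holter ECG) will start 2 hrs prior to dose administration on Day 1". Extractions are scheduled up to 24 h.
- Section 17.4.1 takes the ECG baseline "from the 3 pre-dose time points (45, 30, and 15 min pre-dose) on Day 1".
- ΔQTcF is the primary endpoint (8.1.1). Section 8.2.1 lists "Change-from-baseline heart rate, PR and QRS interval" among the secondary endpoints.

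**The concern.** The protocol sets out to exclude a small QT effect with high-precision ECGs (sections 7.1 and 9.2). It fixes meals, rest, posture and nicotine around the recordings. Coffee is a common xanthine source, and its use is left to each subject on the one day that yields all the endpoint ECGs. No provision for recording it is described.

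The fast makes the exposure uneven over time. If coffee counts as breaking the fast, the baseline and the first 4 h are caffeine-free and the later ECGs are not. If a site takes the view that black coffee is compatible with fasting, the baseline itself is open. The text does not settle which reading applies.

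Caffeine may shift heart rate, and an imperfect Fridericia correction would carry part of that shift into QTcF. The late ECGs enter several analyses:

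- the by-time-point models for ΔHR and ΔQTcF (17.4.4);
- the outlier counts by time point (17.4.5);
- the exposure-response model (17.4.3), where late, low-concentration points help to fix the active-versus-placebo intercept that is added to each prediction at Cmax.

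**Working it through.** **1. Which ECGs lie inside the fast.** Table 1 gives 12 nominal post-dose times from 5 min on: 5, 15 and 30 min, then 1, 2, 3, 4, 5, 6, 8, 12 and 24 h.

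| ECG times | Fast (8 h pre-dose to 4 h post-dose) |
|---|---|
| Baseline: -45, -30, -15 min | inside |
| 5 min to 4 h (7 times) | inside, with 4 h at the boundary |
| 5, 6, 8, 12, 24 h (5 times) | outside |

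So 5/12 = 42% of post-dose times are open to coffee. Dosing is a 3-min i.v. bolus, so parent Cmax falls in the protected window. The primary conclusion is drawn at geometric mean Cmax (17.4.3).

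**2. The plan's own power figure.** Section 17.2 gives 24 active, 9 placebo, SD 7 msec, margin 10 msec, true effect 3 msec and one-sided 0.05.

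- SE = 7 × √(1/24 + 1/9) = 2.74 msec.
- Power = Φ((10 − 3)/2.74 − 1.645) = Φ(0.91) = 0.82. The stated 82% reproduces.
- For 48 versus 18 the same formula gives 0.976, against the stated 97.5%.

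**3. Chance imbalance in heart rate.** The documents give no caffeine figures, so two inputs are assumed: half the subjects drink coffee, and coffee moves heart rate by 3 to 5 bpm at the late points.

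The SD of the difference in the proportion of coffee drinkers is √(0.25/n₁ + 0.25/n₂).

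| Contrast | SD of difference | × 3 bpm | × 5 bpm |
|---|---|---|---|
| One dose vs pooled placebo (8 vs 9) | 0.243 | 0.7 bpm | 1.2 bpm |
| All active vs placebo (24 vs 9) | 0.195 | 0.6 bpm | 1.0 bpm |

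**4. Carry-over into QTcF.** A further assumption is needed: 0.5 to 1 msec of QTcF per bpm. Take the upper 24-versus-9 figure (1.0 bpm) and let it act on the whole design SE. This overstates the effect on the primary estimate, since only late points are touched.

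- 0.5 msec per bpm: √(2.74² + 0.5²) = 2.78 msec (+1.7%). Power = Φ(7/2.78 − 1.645) = 0.81.
- 1 msec per bpm: √(2.74² + 1.0²) = 2.91 msec (+6.5%). Power = Φ(7/2.91 − 1.645) = 0.78.

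**5. Effect on the primary prediction.** I put a 1 msec active-minus-placebo imbalance, confined to 5 to 24 h, through the section 17.4.3 model: concentration, treatment and time as fixed terms, a random intercept per subject, 8 subjects per dose and 9 on placebo. The concentration curve is assumed: biexponential, dose-proportional, scaled to the 23,300 µg/L at 10 min for 500 mg/m² in Appendix 18.3, with a terminal half-life of 1.6 h. Cmax is taken as the 5 min value.

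- The intercept moves by about +0.5 msec.
- The slope moves the other way.
- The prediction at Cmax moves by about +0.2 msec at 200 mg/m², about 0 at 350 mg/m², and −0.2 to −0.3 msec at 500 mg/m².

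These values changed little over four assumed curve shapes and three splits of between- and within-subject variance.

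**The case against.** A reader might infer that the protocol contradicts itself, because it excludes subjects for xanthines and then permits coffee. It does not. Exclusion 14 covers energy drinks in the two days before screening and says nothing about the dosing day. Barring energy drinks while capping coffee is a deliberate choice about two products. The only textual mismatch is a heading wider than the rule beneath it.

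A reader might also infer that caffeine contaminates the whole 24 h Holter and biases the primary result. The documents do not support that either. Read with the water allowance, the fast most naturally keeps coffee out of the baseline and the first 4 h, where Cmax lies. Placebo runs concurrently and blinded within each cohort, and the model's time factor absorbs any average shift after lunch. Chance imbalance in a lifestyle habit is ordinary between-subject variation, which the 90% confidence interval is meant to reflect. Section 17.2 calls its calculation conservative, and nothing shows that the 7 msec SD leaves out normal dietary variation.

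The sizes above rest on assumed inputs, and a ban may itself cause withdrawal headaches in a study that counts AEs.

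All of this stands. It limits the point to noise and clarity. It does not answer the remaining gap: coffee on the ECG day is not regulated, the fast is silent on it, and the noise is easy to avoid in subjects already confined on standardised meals.

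**Conclusion.** The point holds as a modest improvement to the conduct of the study. It is not an error that undermines the primary analysis. Section 10.6.1 leaves coffee open at 5 of the 12 post-dose ECG times and does not say whether coffee breaks the fast. If it does, baseline and the Cmax region are protected, and the cost falls mainly on ΔHR and late ΔQTcF as extra variance and chance imbalance, without systematic bias.

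Under the assumed coffee use and heart-rate shift, the SD of that imbalance is 0.6 to 1.2 bpm. As a deliberately high bound, the SE used for sample size rises by about 2% to 6%, taking power from 82% to between 81% and 78%. On the primary prediction, each 1 msec of late imbalance moves the estimate by no more than about 0.3 msec, against a 10 msec margin. If sites let subjects drink coffee during the fast, baseline would also be exposed; the documents give no basis for sizing that case.

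**What to change.** Reconcile the coffee, xanthine and fasting bullets in section 10.6.1 with a sentence along these lines: coffee and other caffeine-containing drinks count as breaking the fast and are not taken from admission on Day -1 until the 24 h Holter extraction; the limit of five cups a day applies on all other study days.

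If full abstinence is unwanted, the alternative is a fixed amount, identical for all subjects, given at a set time outside the fast and recorded. Either version removes the self-chosen element from the 5 to 24 h ECGs. The xanthine bullet's heading and text should then cover the same products.

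The cost is one sentence and a small change in clinic routine. Abstinence may produce some caffeine-withdrawal headaches that are recorded as AEs. Randomisation balances these in expectation, and the fixed-amount option largely avoids them. Sample size and analysis are unaffected.
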